5.4 TREATMENT REGIMENS

Continuous intravenous infusion of nitroglycerin 5 mcg/min will be started and titrated every 3-5 minutes for a maximum of 100 mcg/minute if tolerated by blood pressure (>100/60mmHg), at least 1 hour before and 3 hours after the procedure. The nitroglycerin for infusion comes in a pre-mixed 250 ml bottle, with a concentration of 200 mcg/ml.

Intravenous sodium chloride 0.9%, will be administered at 1ml/kg/hr at least 1 hours before the procedure and at least 3 hours after for both treatment arms. If the ejection fraction is known to be less than 40% or patient have signs and symptoms of volume overload, a 0.5 ml/kg/hr regimen will be utilized. If the patient is in acute congestive heart failure, no intravenous fluids will be given.

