1.0 EXECUTIVE SUMMARY

Study Design

This is a placebo controlled study in 400 patients, testing the hypothesis that pre-treatment use of intravenous nitroglycerin will decrease the incidence of renal insufficiency after percutaneous angiography, cardiac or lower extremity

Intervention

Patients undergoing percutaneous angiography will be randomly assigned to receive intravenous nitroglycerin (5 mcg/min, titrated up to 50mcg/min for at least 1 hour, maintaining systolic blood pressure (BP) > 100 mmHg, before and 3 hours after the procedure) or a normal saline placebo in a 1:1 ratio.

Enrollment period

The patients will be enrolled during a 2 year period.

Rationale for this study

Animal models suggest that the impaired synthesis of nitric oxide is one important contributor to the pathogenesis of the vasoconstriction caused by exposure to contrast-media. Our previous, retrospective, pilot study supported the hypothesis that the administration of nitrates, particularly intravenous nitroglycerin, before PCI, may decrease the incidence of contrast induced nephropathy (CIN).

Primary Endpoint:

- 1- The primary endpoint will be the change in estimated glomerular filtration rate (eGFR) assessed by modification of diet for renal disease formula, after percutaneous angiography.

Secondary Endpoints:

- 1- CIN will be defined as an increase in serum creatinine of 25% or ≥ 0.5 mg/dl post-percutaneous angiography.
- 2- Safety profile of the intervention including volume overload, hypotension, headache, the need for hemodialysis, intra-aortic balloon pump, endotracheal intubation or the use of pressors.
- 3- Analysis and comparison to a CIN predictive score calculator (Mehran Score).

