5.2.3 EXCLUSION CRITERIA

None of the following exclusion criteria must be present for the patient to be enrolled in the trial

- 1- Patients on renal replacement therapy before randomization, will be excluded.
- 2- Being exposed to any types of nitrates 48 hours prior to randomization,
- 3- History of allergic reaction to any of the components of intravenous nitroglycerin.
- 4- Exposure to contrast media 4 days prior randomization.
- 5- Planned revascularization in the next 24 to 48 hours of the first PCI procedure.
- 6- The patient is hypotensive (<90/60mmHg) at the time of randomization.
- 7- Patients exposed to phosphodiesterase inhibitors 48 hours prior to randomization

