5.2.4 SCREENING AND BASELINE EVALUATION

Potentially eligible patients will undergo an initial evaluation in which eligibility will be confirmed and the trial protocol explained in detail. All willing and eligible patients providing informed consent will have baseline data obtained including relevant history and use of all conventional and alternative therapies. Baseline laboratory tests will be performed and information on quality of life will be obtained.

The following variables will be obtained for all patients included in the trial: age, gender, weight, height, body mass index, blood pressure, left ventricular ejection fraction, hypertension, diabetes mellitus, peripheral vascular disease, medication use (angiotensin converting enzyme inhibitors, calcium channel blockers, beta blockers, statins, ascorbic acid, acetylcysteine, angiotensin receptor blockers, diuretics, aspirin), PCI (number of vessels) smoking status, amount of contrast, type of contrast, amount of hydration, serum hemoglobin, serum sodium, serum potassium, baseline creatinine and post procedure creatinine, glomerular filtration rate.

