5.3 STUDY ALGORythM

To achieve our primary and secondary end-points we will (1) screen patients in the catheterization lab and/or emergency department of Mount Sinai Medical Center. (2) After inclusion and exclusion criteria's are verified, informed consent will be signed by the patient. (3) a case report form will be completed. (4) The research staff will order a treatment protocol to be administered. (5) Laboratory studies will be performed if needed. (6) The patients will receive an intravenous infusion of nitroglycerin and/or saline for at least 1 hour. (7) Coronary angiography will be performed and another screening for exclusion criteria will be done by the coordinator and assistant investigators. (8) Variables such as volume of contrast and number of vessels stented will be obtained. (9) Patients will go to recovery area and another infusion will be started for another 3 hours. (10) 48 hours later patient will be contacted to come to the hospital for another set of laboratory studies or patients that stayed in the hospital will be contacted and all the information needed will be completed.

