5.4.1 NITROGLYCERIN PHARMACOLOGY

Nitroglycerin is a vasodilator and antianginal agent, that can be administer intravenously, orally, intra-anal, as a topical agent, as a patch, sublingual and as a translingual spray. In our study it will be administered via intravenous infusion as previously specified by the protocol.

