5.4.1.2 SEVERE HYPOTENSION

The most common adverse effect of Nitroglycerin is hypotension. Nitroglycerin forms free radical nitric oxide. In smooth muscle, nitric oxide activates guanylate cyclase which increases guanosine 3'5' monophosphate (cGMP) leading to dephosphorylation of myosin light chains and smooth muscle relaxation. This produces a vasodilator effect on the peripheral veins and arteries with more prominent effects on the veins, decrease preload (left ventricular end-diastolic pressure); may modestly reduce afterload. This can lead to severe hypotension and paradoxical bradycardia and increased angina pectoris can accompany hypotension.

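### The protocol states two maximum nitroglycerin rates, 50 and 100 mcg/min, with different blood pressure conditions, and does not say which governs

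*Combined protocol and SAP*

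**What the plan says.** The infusion is specified in two places.

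- **Section 1.0, Executive summary (Intervention).** Starting at 5 mcg/min, nitroglycerin is "titrated up to 50mcg/min for at least 1 hour, maintaining systolic blood pressure (BP) > 100 mmHg".
- **Section 5.4, Treatment regimens.** Starting at 5 mcg/min, it is "titrated every 3-5 minutes for a maximum of 100 mcg/minute if tolerated by blood pressure (>100/60mmHg"), for at least 1 hour before and 3 hours after the procedure.

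The other sections do not choose between them. Section 5.4.1 says only: "In our study it will be administered via intravenous infusion as previously specified by the protocol". Section 5.3 says: "The research staff will order a treatment protocol to be administered", without a rate or a blood pressure limit. For the second infusion it adds: "Patients will go to recovery area and another infusion will be started for another 3 hours".

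Three further statements bear on the point. Section 5.4.1.2 states: "The most common adverse effect of Nitroglycerin is hypotension". Section 5.2.3 excludes a patient on this criterion: "The patient is hypotensive (<90/60mmHg) at the time of randomization". The variable list in section 5.2.4 includes "amount of contrast, type of contrast, amount of hydration", but no nitroglycerin rate or dose.

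**The concern.** A trial of one drug needs one definition of how that drug is given. Here two orders, one written from the summary and one from section 5.4, would both comply with the protocol, yet they could stop titration at rates a factor of two apart and on different blood pressure readings.

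Two things are at stake. The first is safety: hypotension is described as the drug's most common adverse effect and is part of the safety secondary endpoint in section 4.2. The second is interpretation: if both versions were used, differences between nitroglycerin patients in hypotension or in eGFR change (the primary endpoint) could partly reflect which section was followed. The variables listed in section 5.2.4 would not show which ceiling a patient had been given.

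**Working it through.** **Side by side**

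| | Section 1.0 | Section 5.4 |
|---|---|---|
| Starting rate | 5 mcg/min | 5 mcg/min |
| Maximum rate | 50 mcg/min | 100 mcg/min |
| Systolic condition | > 100 mmHg | > 100 mmHg |
| Diastolic condition | none stated | > 60 mmHg |
| Titration interval | none stated | 3-5 minutes |

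A reading of 110/55 mmHg meets the first blood pressure condition and fails the second.

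**Figures that follow from stated inputs.** The concentration is 200 mcg/ml (section 5.4) and the minimum infusion time is 1 + 3 = 4 hours, or 240 minutes.

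- Pump rate at the ceiling = mcg/min × 60 / 200: 50 × 60 / 200 = 15 ml/h, and 100 × 60 / 200 = 30 ml/h.
- Upper bound on total dose, with the ceiling held from minute 0: 50 × 240 = 12,000 mcg = 12 mg, and 100 × 240 = 24,000 mcg = 24 mg.

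**Allowing for up-titration.** The step size is not stated. Steps of 5 and 10 mcg/min are assumed for arithmetic only, and section 5.4's 3-5 minute interval is applied to both ceilings. The rate at minute m is min(cap, 5 + step × floor(m / interval)), summed per minute.

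Example for the first 60 minutes, with 5 mcg/min steps every 3 minutes:

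- Cap 50 is reached at 27 minutes: 3 × (5 + 10 + … + 45) + 33 × 50 = 675 + 1,650 = 2,325 mcg.
- Cap 100 is reached at 57 minutes: 3 × (5 + 10 + … + 95) + 3 × 100 = 2,850 + 300 = 3,150 mcg.

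Section 5.3 has another infusion started in recovery but does not say at what rate. The 4-hour total is therefore given both ways: restarted at 5 mcg/min, and carried on from the rate reached. Entries are mg under the 50 cap versus the 100 cap, with the ratio in brackets.

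| Step, interval | First 60 min | 4 h, restarted | 4 h, carried on |
|---|---|---|---|
| 5 mcg/min, 5 min | 1.875 vs 1.950 (1.04) | 9.75 vs 15.20 (1.56) | 10.88 vs 19.25 (1.77) |
| 5 mcg/min, 3 min | 2.325 vs 3.150 (1.35) | 10.65 vs 18.30 (1.72) | 11.33 vs 21.15 (1.87) |
| 10 mcg/min, 5 min | 2.375 vs 3.500 (1.47) | 10.75 vs 19.00 (1.77) | 11.38 vs 21.50 (1.89) |
| 10 mcg/min, 3 min | 2.625 vs 4.500 (1.71) | 11.25 vs 21.00 (1.87) | 11.63 vs 22.50 (1.94) |

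In the hour before the procedure the gap can be as small as 4%. Over the 4 hours it is at least 56% in a patient who tolerates titration to the ceiling. It is zero in a patient whose blood pressure stops titration at or below 50 mcg/min.

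**Entry rule against on-treatment rule.** A patient with systolic pressure of 90-100 mmHg can pass the hypotension exclusion and be randomised while meeting neither on-treatment condition. The protocol does not say how such a patient is handled.

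**The case against.** The strongest reply is that section 5.4 is the detailed treatment section, and that section 5.4.1, which sits directly beneath it, can be read as pointing to it. That reading is natural, but it is not a precedence rule: the summary states its own ceiling under Intervention without deferring to section 5.4. A few pages are absent from the text available for review, so the lack of a precedence rule is established for the available text only. A rule elsewhere would still leave two maxima in the protocol.

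A second reply is that this is a single centre with a study coordinator who orders the treatment (section 5.2.5), so one order may be used throughout. That is possible, and mixed use of the ceilings is a risk rather than a demonstrated fact. Dose also varies by design, because it is titrated to blood pressure. Mixed ceilings would blur which regimen was tested but would not in themselves invalidate the randomised comparison.

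Several narrower points are fair:

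- The blood pressure difference is a diastolic limit missing from a summary, which is weaker than the conflict in dose.
- An entry criterion may legitimately differ from an on-treatment condition, and section 5.4 does hold back titration below its limit. What stays open is whether the infusion is started at all in the 90-100 mmHg group.
- Section 5.2.4 is a baseline list and the case report form was not supplied, so dose may be recorded elsewhere.
- The modelled totals depend on an assumed step size. Only the pump rates and the 12 versus 24 mg bound follow from stated figures.

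None of this removes the conflict between 50 and 100 mcg/min.

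**Conclusion.** The concern holds and must be fixed. Two current sections give maximum rates that differ by a factor of two, and nothing in the available text decides between them. This conflict alone carries the rating. The diastolic mismatch is a sub-point, and the unstated handling of systolic 90-100 mmHg is secondary.

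The practical size depends on tolerance and titration speed: 4-hour ratios of 1.56 to 1.94 under the assumed steps, for patients who reach the ceiling. The sample size in section 5.1 is unaffected, because its assumed relative risk of 0.5 is not tied to a dose.

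A minor related item: section 5.4.1.4 places ergot derivatives in its category X (combination to be avoided), but the exclusion list in section 5.2.3 does not address them, although it does cover phosphodiesterase inhibitors.

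**What to change.** The sponsor must reconcile sections 1.0 and 5.4. The documents give no basis for choosing between the two dose limits or the two blood pressure conditions, and no preference is expressed here. In one amendment:

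1. State one maximum rate and one blood pressure condition, identically in sections 1.0 and 5.4.
2. Carry both into the treatment order mentioned in section 5.3, and have section 5.4.1 cite the governing section by number.
3. Reconcile the entry criterion in section 5.2.3 with the on-treatment condition by stating how randomised patients with systolic pressure of 90-100 mmHg are handled.
4. Add the delivered nitroglycerin rate and total dose to the variable list in section 5.2.4.
5. As a minor item, reconcile the exclusion list with the protocol's own category X interactions.

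The cost is a wording amendment, a matching infusion order and two data fields, with no added visits or tests.

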2.0 BACKGROUND

2.1 INTRODUCTION

CIN is a complication of percutaneous angiography that, when it occurs, usually begins shortly after the administration of contrast media (1-3). The incidence has been reported in the range of 0 to 50%, depending on comorbidities and risk factors (4-8). CIN usually resolves spontaneously, but it has been associated with an increased risk of morbidity, in-hospital death, and late mortality (9-10). There is no specific management for renal insufficiency after the development of CIN. Therefore, there is interest in finding preventive strategies. Available evidence supports the use of hydration, sodium bicarbonate, and reduction of contrast volume administered to patients at risk (22). Statin use for prevention of CIN is still controversial (30-32), with a recent publication showing promising results (33). A hydration system was proposed by Briguori et al. (34) that showed CIN preventive effects. Further studies are needed to support these findings. Other agents, such as N-acetylcysteine, fenoldopam, nifedipine, captopril, prostaglandins and aminophylline have been evaluated in the prevention of CIN with varying results (23-29).

Animal models suggest that the impaired synthesis of nitric oxide is one important contributor to the pathogenesis of the vasoconstriction that may lead to CIN (11-13). We plan to investigate whether the use of intravenous nitroglycerin before exposure to contrast media reverses this vasoconstriction, and therefore, prevents the development of CIN.

The present manuscript describes the background, rationale, study design, safety monitoring, and analysis plan for the proposed contrast nephropathy and nitrates trial (CoNaN).

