5.0 RESEARCH DESIGN AND METHODS

5.1 SAMPLE SIZE

NOT A CASE CONTROL STUDY. This is a randomized, placebo-controlled clinical trial with a 1:1 randomization of active therapy to placebo. Prior data from our retrospective study indicate that the failure rate among controls is 0.3. If the true relative risk of failure for experimental subjects relative to controls is 0.5, we will need to study 161 experimental subjects and 161 control subjects to be able to reject the null hypothesis that this relative risk equals 1 with probability (power) 0.9. The Type I error probability associated with this test of this null hypothesis is 0.05.

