5.2.5 RANDOMIZATION

After inclusion and exclusion criteria verification, coordinator will complete the randomization screen, in the system. The patients will be randomly assigned to one of the two treatment arms. The coordinator will order the treatment in the patient's chart and start the pre-stocked infusion. The infusions will consist in intravenous nitroglycerin in addition to Intravenous Saline or Intravenous saline.

We will randomize using a computer generated pre-set list. The computer program will randomly assign a letter (A or B) to each individual case up to 400 cases. The trial coordinator and the pharmacist will be the only un-blinded persons that will have access to the randomization list. In case that for safety reasons an investigator must know if the patient is receiving the experimental therapy or not, a copy of the randomization list will be held at the coordinator's office.

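### The saline level is not fixed before randomisation, and un-blinded staff order treatment after it, so knowledge of allocation can influence background hydration

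*Combined protocol and SAP*

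**What the plan says.** Section 5.4 prescribes background saline for both arms at a standard rate of 1 ml/kg/hr. There are two departures from that rate.

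- **Reduced level.** It applies if the ejection fraction is known to be below 40%, or if the "patient have signs and symptoms of volume overload, a 0.5 ml/kg/hr regimen will be utilized". The second trigger is not defined.
- **No fluid.** "If the patient is in acute congestive heart failure, no intravenous fluids will be given".

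The duration is given as "at least 1 hours before the procedure and at least 3 hours after for both treatment arms", with no upper limit. Section 5.3 instead describes the post-procedure infusion as lasting a further three hours.

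On sequence and staff, Section 5.2.5 has the coordinator complete the randomisation screen, after which the patient is assigned. Then: "The coordinator will order the treatment in the patient's chart and start the pre-stocked infusion". The same section states: "The trial coordinator and the pharmacist will be the only un-blinded persons that will have access to the randomization list". Section 5.3 attributes the ordering to research staff in general. No section says who selects the saline level, when it is assessed, or whether it may be revised.

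Section 2.1 treats hydration as effective: "Available evidence supports the use of hydration, sodium bicarbonate, and reduction of contrast volume administered to patients at risk". Section 5.2.4 lists the amount of hydration among the variables collected. No comparison of it between arms is planned.

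**The concern.** The trial asks whether nitroglycerin protects the kidney. Hydration is a competing protective measure by the protocol's own account, so the arms should be hydrated under the same decisions. Part of the decision is an undefined clinical judgement, it may be made after assignment, and the person who orders treatment knows the arm. That leaves room for allocation to influence how much prophylaxis a patient receives.

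There is a second, conditional route. Section 5.3 starts another infusion in recovery, when a nitroglycerin patient has already had at least an hour of drug. If the saline level is reassessed then, the drug may have changed the signs on which it depends. Section 5.4.1.2 says nitroglycerin acts to "decrease preload (left ventricular end-diastolic pressure); may modestly reduce afterload", which could make overload less apparent. Section 5.4.1 also lists edema as a common reaction, which could do the opposite.

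The two routes differ in meaning. A fluid change that truly follows from what the drug did to the patient is part of the effect of assignment. A change driven by knowing the arm is bias.

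The decision is unlikely to be rare. In Section 4.2.1, congestive heart failure (which includes an ejection fraction below 40%) supplies 5 of the 6 Mehran points needed for entry. Section 5.2.3 does not exclude acute heart failure.

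**Working it through.** **1. The plan's own figure.** Section 5.1 states: "Prior data from our retrospective study indicate that the failure rate among controls is 0.3". It also gives a relative risk of 0.5 (so 0.30 against 0.15), power 0.9, type I error 0.05 and 161 per arm. Taking the test as two-sided, without continuity correction:

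n = [1.960 × √(2 × 0.225 × 0.775) + 1.282 × √(0.30 × 0.70 + 0.15 × 0.85)]² / 0.15² = 160.8, so 161.

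The figure reproduces and is not in dispute. At 200 per arm (400 enrolled) power is 0.951.

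**2. Saline volume at stake.** Body weight is assumed. The minimum is 1 + 3 = 4 hours, excluding procedure time. Volume = rate × weight × 4.

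| Weight | Standard | Reduced | None |
|---|---|---|---|
| 60 kg | 240 ml | 120 ml | 0 |
| 80 kg | 320 ml | 160 ml | 0 |
| 100 kg | 400 ml | 200 ml | 0 |

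Because Section 5.4 sets only minimums, 8 hours at the standard rate for 80 kg would be 640 ml and would still comply.

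**3. Volume carried by the drug.** Section 5.4 gives 200 mcg/ml. The documents give two ceilings, 50 mcg/min (Section 1.0) and 100 mcg/min (Section 5.4), which themselves must be reconciled.

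- 50/200 × 60 = 15 ml/h, or 60 ml over 4 h.
- 100/200 × 60 = 30 ml/h, or 120 ml over 4 h.
- At the starting rate of 5 mcg/min: 5/200 × 60 = 1.5 ml/h, or 6 ml over 4 h.

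The 60 to 120 ml is therefore an upper bound, reached only if the ceiling applied throughout.

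**4. Possible bias in CIN if nitroglycerin has no effect.** The documents give no tier shares and no tier-specific risks, so both are assumed. Let q0 and q1 be the shares at the reduced level in the control and nitroglycerin arms, and k the ratio of CIN risk at the reduced level to that at the standard level. Control risk p0 is held at 0.30.

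- Standard-level risk: p_s = 0.30 / (1 − q0 + k·q0)
- Nitroglycerin-arm risk: p1 = p_s × (1 − q1 + k·q1)
- With d = p0 − p1, p̄ the mean of p0 and p1, SE0 = √(2p̄(1 − p̄)/n) and SE1 = √([p0(1 − p0) + p1(1 − p1)]/n), rejection = Φ[(d − 1.96·SE0)/SE1] + Φ[(−d − 1.96·SE0)/SE1], n = 200.

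Example: q0 = 0.30, q1 = 0.20, k = 1.5. Then p_s = 0.30/1.15 = 0.261, p1 = 0.261 × 1.10 = 0.287, relative risk 0.957, d = 1.3 points, rejection 5.9%.

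Spurious relative risk, and two-sided rejection at a nominal 5%:

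| Reduced level, control vs nitroglycerin | k = 1.25 | k = 1.5 | k = 2.0 |
|---|---|---|---|
| 30% vs 20% | 0.977; 5.3% | 0.957; 5.9% | 0.923; 8.0% |
| 30% vs 10% | 0.953; 6.1% | 0.913; 8.9% | 0.846; 17.8% |
| 40% vs 10% | 0.932; 7.4% | 0.875; 13.2% | 0.786; 30.5% |
| 20% vs 30% | 1.024; 5.3% | 1.045; 6.0% | 1.083; 8.4% |

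In the first three rows d runs from 0.7 points (p1 = 0.293) to 6.4 points (p1 = 0.236), against the planned 15. The table treats the whole imbalance as allocation-driven and the tier risks as caused by hydration. It leaves out the no-fluid level. The same calculation cannot be done for the primary endpoint, because the documents give no expected eGFR change or variance.

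**The case against.** Several stronger readings are tempting, and the documents do not support them.

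- **That the coordinator chooses the saline level.** No section says so. Section 5.2.5 has the coordinator order and start treatment, Section 5.3 refers to research staff, and the coordinator's duties in Section 3.2 include no hydration decision. What stands is that no one is named and nothing keeps the choice away from un-blinded staff.
- **That the duration is open-ended.** Section 5.4 sets only minimums, but Section 5.3 and the executive summary give three hours after the procedure. What stands is a mismatch to reconcile.
- **That nitroglycerin alters the judgement.** At the first order no study drug has been given, and Section 5.2.3 excludes nitrate exposure in the preceding 48 hours. A drug effect requires a later reassessment, which Section 5.4 does not describe, and it could go either way. The ejection-fraction trigger is a pre-existing value that the drug does not change.
- **That the result could not be attributed to nitroglycerin.** The working does not bear this out for a modest imbalance, and under intention to treat a fluid change caused by the drug belongs to the effect of assignment.
- **That the drug adds a large unmatched volume.** The figures are ceilings. Section 1.0 calls the control a saline placebo, so whether its volume is matched is unclear.

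It may also be said that the acute heart failure rule is simply a specific exception to the general statements in Sections 4.3 and 5.2.5. That is a fair reading, and the repair is mostly one of wording. Finally, hydration is recorded, but this only describes an imbalance afterwards. Volume received is a post-randomisation variable, so adjusting for it would not restore the comparison.

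**Conclusion.** The point holds in a limited form. The saline level is not fixed before randomisation, one of its triggers is undefined, no one is named to choose it, and treatment is ordered after assignment by someone who knows the arm. Allocation can therefore influence a background measure that the protocol regards as protective. That it will do so is not shown.

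The size is unknown. Under the assumed tier shares and risks, a 10-point imbalance moves the false-positive rate for CIN from 5% to at most 8.4% in either direction. Inflation to 17.8% or 30.5% needs an imbalance of 20 or 30 points together with doubled risk at the reduced level. The sample size is unaffected. The case for acting rests on how cheaply the gap can be closed, not on a demonstrated large bias.

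**What to change.** None of these changes selects a rate or a clinical rule.

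1. In Sections 5.2.4 and 5.2.5, have an investigator without access to the randomisation list record the saline level and planned saline duration on the case report form before the randomisation screen is opened. Later changes for clinical need remain possible. Where possible they should be decided by staff without list access, and each should be logged with reason and time and reported by arm.
2. Use the pre-randomisation level, not the volume received, for any adjustment or subgroup. Report total intravenous volume, including the drug infusion, by arm as description only.
3. Reconcile the post-procedure duration in Section 5.3 with the minimum in Section 5.4. Reconcile the no-fluid statement for acute heart failure in Section 5.4 with Sections 4.3 and 5.2.5, which give every patient saline.

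The cost is protocol wording, a few case report form fields and one more entry before randomisation by existing staff. This removes allocation-driven choice at the first order. It limits, but does not remove, the same risk at later changes.
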